## **7.2 Treatment exposure and compliance**

All immunosuppressant drug levels will be documented at the study time points, and compliance with the dosing will be assessed at each study time point by the PI and coordinator. Side effects of tacrolimus (renal, neurologic, metabolic, etc) and everolimus (hyperlipidemia, edema, proteinuria, etc) will be documented in the case report forms

## **7.3 Efficacy**

The major efficacy assessment is the percentage of patients successfully withdrawn from TAC therapy in favor of EVL therapy without rejection or major complications. Rejection will be evaluated by liver biopsy when indicated (typically 2-3 fold increase in liver aminotransferases). If rejection occurs during any point of the trial following EVL addition, the study will be terminated for that patient.

Other efficacy endpoints will be the improvement in TAC side effects (renal, neurologic, metabolic, etc.) and development of EVL side effects (hyperlipidemia, edema, proteinuria, etc) in those successfully withdrawn from TAC without rejection. For those unable to withdraw from TAC due to rejection, we will assess for TAC side effects and EVL side effects if this drug is continued following rejection. Liver and renal function, and hematological parameters will be followed per SOC throughout this biomarker study

The PI and research coordinator will perform these assessments at the study time points at Northwestern and at any intervening time point if the patient needs a liver biopsy to exclude rejection or other complication (hospitalization, infection, etc.). Patients enrolled also will be contacted by phone for any changes in their immunosuppression dosing or other medications in between visits.

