## Glossary of terms

Assessment	A procedure used to generate data required by the study
Control drug	A study drug used as a comparator to reduce assessment bias, preserve blinding of investigational drug, assess internal study validity, and/or evaluate comparative effects of the investigational drug
Enrollment	Point/time of patient entry into the study; the point at which informed consent must be obtained (i.e. prior to starting any of the procedures described in the protocol)
Investigational drug	The study drug whose properties are being tested in the study; this definition is consistent with US CFR 21 Section 312.3 and is synonymous with "investigational new drug."
Medication number	A unique identifier on the label of each medication package in studies that dispense medication using an IVR system
Patient number	A number assigned to each patient who enrolls in the study. When combined with the center number, a unique identifier is created for each patient in the study.
Stage	A major subdivision of the study timeline; begins and ends with major study milestones such as enrollment, randomization, completion of treatment, etc.
Period	A minor subdivision of the study timeline; divides phases into smaller functional segments such as screening, baseline, titration, washout, etc.
Premature patient withdrawal	Point/time when the patient exits from the study prior to the planned completion of all study drug administration and assessments; at this time all study drug administration is discontinued and no further assessments are planned
Randomization number	A unique identifier assigned to each randomized patient, corresponding to a specific treatment arm assignment
Stop study participation	Point/time at which the patient came in for a final evaluation visit or when study drug was discontinued whichever is later
Study drug	Any drug administered to the patient as part of the required study procedures; includes investigational drug and any control drugs
Study drug discontinuation	Point/time when patient permanently stops taking study drug for any reason; may or may not also be the point/time of premature patient withdrawal
Variable	Information used in the data analysis; derived directly or indirectly from data collected using specified assessments at specified time points

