### 3.2 Secondary endpoints

Clinical endpoints as correlates for the success and failure of TAC-WD/EVL will serve as clinical secondary endpoints. This will include but not be limited to the following at 6 months ( $\pm$  1 month) post-LT: liver allograft and renal function, EVL & TAC side effects, infectious/malignant complications, and patient/graft survival. At study end, all secondary endpoints will be statistically compared between those who succeed or fail TAC-WD/EVL.

The other mechanistic biomarker endpoints tested potentially in the future (unfunded exploratory objectives) will focus on comparing biopsy and peripheral blood microarray signatures at the time of a rejection biopsy, comparing these biopsy signatures in rejections that occur before and after TAC-WD, and other predictive biomarkers (miRNA, DSA, proteomic, donor specific assays- see exploratory objectives below).

The primary safety endpoints are the development of rejection with TAC-WD and any graft failure due to rejection, the latter of which is not expected to happen based on the registration studies. We expect that 20% of patients will experience rejection that is reversible with resumption of TAC +/- corticosteroids, without any graft loss, all based on the registration studies. However, if any patient experiences a graft loss due to the protocol (TAC-WD) or  $\geq 30\%$  rejection is seen, the study will be terminated due to safety concerns.

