### 6.3.7 Study drug discontinuation and premature patient withdrawal

Subjects may be withdrawn from the trial at any time for any reason, either by choice or due to medical indications. Subjects who are non-compliant with study guidelines, medications and clinic examinations will be withdrawn from the study. The NU IRB may also discontinue the study at any point. The subjects will be fully informed of these actions. If patients are withdrawn prematurely, they will still be followed through the follow-up time period of the study as per standard medical care. These data are important to collect to determine differences in this group compared to those who completed the study.

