## 7 Visit schedule and assessments

**Table 7-1 Assessment schedule**

Visit**	1	2	3	4	5	6	7	At rejection***	Early Term./Study Comp.
Day	-90 to 0 +30 (Tx)	0	30	90	120	135	180		
Inc./Exc. Criteria	X		X	X	X				
Obtain informed consent	X								
Physical Exam			X	X	X		X		
Donor/Recipient Collections		X*							
Blood (Flow, PBMC, RNA, sera)			X*	X	X	X	X	X	
Tissue RNA								X	
Study Completion Form						X	X		X

\*unfunded and not mandatory for this protocol

\*\*  $\pm$  1 month window allowable

Visit 1 = Patient enrollment SOC visit (I/E criteria, informed consent)

Visit 2= Transplant SOC- if possible, donor spleen/lymph nodes and recipient lymph node/blood

Visit 3= Day 30 SOC visit- if Inc./Exc. criteria met, add everolimus and stop MPA if being used. Collect blood if possible (unfunded for this study).

Visit 4= Day 90 SOC visit- if Inc./Exc. criteria met, start tacrolimus withdrawal. Collect blood.

Visit 5= Day 120 SOC visit- if Inc./Exc. criteria met, stop tacrolimus. Collect blood.

Visit 6 = Day 135 visit- collect blood.

Visit 7= Day 180 SOC visit- Study termination. Collect blood.

\*\*\*At any biopsy concerning for rejection: Collect blood and tissue in RNAlater. If rejection, study termination.

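### The plan contradicts itself on follow-up after rejection, so it is unclear whether the failed group will have month-6 data for the secondary comparisons

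*Combined protocol and SAP*

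**What the plan says.** **Participation ends at rejection.** Section 7.3: "If rejection occurs during any point of the trial following EVL addition, the study will be terminated for that patient". The Table 7-1 footnote on biopsies for suspected rejection: "If rejection, study termination". The glossary, on premature patient withdrawal: "at this time all study drug administration is discontinued and no further assessments are planned".

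**Follow-up continues.** Section 6.3.7: "If patients are withdrawn prematurely, they will still be followed through the follow-up time period of the study as per standard medical care". It gives the reason: "These data are important to collect to determine differences in this group compared to those who completed the study". Section 7.3, in the paragraph after the termination sentence: "For those unable to withdraw from TAC due to rejection, we will assess for TAC side effects and EVL side effects". The everolimus part applies only if that drug goes on after rejection, and no time point is given.

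**What is compared.** Section 3.2 sets the secondary endpoints at 6 months (±1 month) post-transplant: graft and kidney function, drug side effects, infection and malignancy, and patient and graft survival. It then says: "At study end, all secondary endpoints will be statistically compared between those who succeed or fail TAC-WD/EVL". Section 10.3 repeats this. Section 10.3.1 calls the clinical outcomes mainly descriptive but still plans tests between the two groups.

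**Where the clinical data come from.** Section 4 describes a routine month-6 clinic visit, with lipids, HbA1C and urine protein/creatinine measured then. Section 7.4.4 describes weekly blood counts, chemistry and drug troughs in months 3-6. All of this is standard of care.

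**The concern.** The event that puts a patient in the failed group is also the event that ends that patient's participation. If termination means that data collection stops, one side of every secondary comparison may lack values at the time the endpoint is defined. If 6.3.7 governs, the data exist and need only be recorded. Two coordinators could each follow the protocol and deliver different datasets.

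There is a second risk. Where the only value available in a failed patient is the one taken at rejection, an analyst may use it as the month-6 value. Section 7.3 says biopsy is typically prompted by a 2-3 fold aminotransferase rise. Liver tests at that moment are therefore abnormal by selection, and setting them against routine month-6 values in successes largely restates the definition of failure. For kidney function, the comparison would mix different times after transplant and different tacrolimus exposure.

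**Working it through.** **1. Size of the group.** Sections 5 and 10.4 expect 20 of 25 enrolled patients to enter withdrawal. Expected failures = 20 × rejection rate.
- At the 20% of section 3: 20 × 0.20 = 4 failures and 16 successes.
- At 25%: 20 × 0.25 = 5 and 15, the split in Figure 6.

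Section 10.4 states 4-5 and 14-15, so the group at issue is 4-5 patients.

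**2. The two readings side by side.**

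| Question | 7.3 termination sentence, Table 7-1 footnote, glossary | 6.3.7, 7.3 side-effect sentence |
|---|---|---|
| Participation after rejection | Ends | Followed through the study period |
| Month-6 data recorded | None required | Intended for comparison with completers |
| Failures with a recorded month-6 value | 0 of 4-5, except a rejection inside the window | Up to 4-5 of 4-5 |

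No sentence says whether termination for rejection is the premature withdrawal that 6.3.7 covers. Section 10.2.3 says discontinuation will usually be due to rejection, but gives no rule for these patients' later data.

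**3. Timing.** Table 7-1 puts the start of the taper at day 90, the tacrolimus stop at day 120 and Visit 7 at day 180. Taking a month as 30 days, the month-6 window is 180 ± 30 = days 150-210.
- Rejection during the taper (days 90-120): 180 - 90 = 90 to 180 - 120 = 60 days before Visit 7, outside the window.
- Rejection at day 135: 180 - 135 = 45 days before Visit 7, outside the window.
- Rejection 1-2 months after the stop: 120 + 30 = day 150 to 120 + 60 = day 180, inside the window.
- The stop has its own ±1 month. A stop at day 90 moves that last range to days 120-150, outside the window except for its final day. A stop at day 150 moves it to days 180-210, inside.

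Section 3 expects rejection in the 1-2 month period after withdrawal. If that means any time up to two months after the stop, the nominal range is days 120-180 and part of it lies outside the window.

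**4. Whether safety reporting fills the gap.** Section 8.2 requires reporting of new SAEs until four weeks after participation stops; later ones are reported only if attributed to study drug. If participation stops at rejection, the window closes at day 120 + 28 = 148 or day 135 + 28 = 163, both before day 180. The glossary dates the end of participation at the later of the final evaluation and the drug stop, so the window is longer where everolimus continues. Neither version yields eGFR, lipids, HbA1C or urine protein/creatinine.

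**5. What losing failures would cost (illustration).** The plan gives no power and no alpha for these tests. Assume a two-sample t-test, two-sided alpha 0.05 and 80% power. The detectable difference d, in SD units, solves P(T > t at 0.975) = 0.80, where T is noncentral t with n1 + n2 - 2 degrees of freedom and noncentrality d × √(n1·n2/(n1 + n2)). For 15 vs 5 the multiplier is √(75/20) = 1.94.

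| Successes vs failures with data | Detectable difference |
|---|---|
| 16 vs 4 | 1.66 SD |
| 15 vs 5 | 1.53 SD |
| 15 vs 3 | 1.89 SD |
| 15 vs 2 | 2.26 SD |
| 15 vs 0 | not estimable |

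**The case against.** The strongest reply is that the data are already planned. Section 6.3.7 covers withdrawal for medical reasons and gives comparison with completers as the purpose of continued follow-up. Section 10.2.3 makes rejection the usual reason for discontinuation, so rejecters look like the main group that 6.3.7 serves. The glossary definition assumes that all study drug has stopped, whereas 7.3 allows everolimus to continue after rejection, so it may not fit these patients. Standard-of-care tests run to month 6, and no section excludes rejecters from them.

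Most of this stands, and it defeats a stronger reading that the termination sentence invites: that the failed group has no planned month-6 assessment and the comparison is about 15 against 0. The documents do not support that. Nor can it be drawn from the sparse early-termination column of Table 7-1. That table lists no clinical laboratory tests or side-effect review at any visit, even Visit 7 for successes, and section 7.4.1 adds an examination at early termination. Rejections 1-2 months after a nominal day-120 stop also fall inside the month-6 window.

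A reader might also infer that the plan intends rejection-time values to stand in for month-6 values. No text says so; the plan only fails to rule it out.

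The reply does not remove the contradiction. Values in a medical chart are not trial data until something requires their entry on the CRF. The 7.3 side-effect sentence has no time attached, and the assessments in 7.2 and 7.3 are tied mainly to study time points, of which a terminated patient has none left in Table 7-1.

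**Conclusion.** The concern holds as an unresolved contradiction about follow-up after rejection. It affects all 4-5 expected failures: their recorded month-6 data could range from none to complete, depending on which section is followed. A rejection-time value that falls inside the window (nominal days 150-180) could also enter as the month-6 value and bias the liver-function comparison.

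Severity is moderate. The primary objective concerns biomarkers, and the clinical endpoints are mainly descriptive secondary outcomes in an unpowered pilot. Even with all five failures observed, the illustrative test detects only differences of about 1.5 SD. A descriptive month-6 summary of the failed group still needs month-6 values, however, and 10.3.1 does plan formal comparisons. The timing rests on nominal visit days and 30-day months; the detectable differences rest on the assumed test, alpha and power.

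**What to change.** - Reconcile section 7.3, the Table 7-1 footnote and the glossary with 6.3.7. State that rejection ends scheduled research blood draws but not clinical data collection, and that 6.3.7 applies to patients who reject.
- Require CRF entry of month-6 standard-of-care data for these patients: eGFR, liver tests, lipids, HbA1C, urine protein/creatinine, side effects, infection and malignancy, and patient and graft survival. Show this in Table 7-1.
- In 10.3, compare successes and failures on values at the common month-6 time. Report rejection-time values separately, and state that they do not substitute for the month-6 value even when they fall inside the window.

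The cost is amendment wording and CRF entry for about 5 patients. The month-6 visit and tests are already standard of care. No treatment rule is proposed or changed.

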**Efficacy assessments:**

- The proportion of patients who are successfully withdrawn from TAC and continued on EVL without rejection or other complications at six months ( $\pm$  1 month) post-LT.
- The following assessments following addition of EVL at one to two months and attempted withdrawal of TAC between 3-6 months ( $\pm$  1 month) in favor of EVL maintenance: liver allograft and renal function, EVL & TAC side effects and discontinuations, infectious/malignant complications, and patient/graft survival.

- Biomarker assessments: Peripheral blood Treg% (or other immunoregulatory cells) and messenger ribonucleic acid (mRNA) AR signatures seen prior to and during either successful (no rejection) vs. failed (rejection) TAC-WD/EVL.

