## **7.4 Safety/Potential Adverse Events/Protection Against Risk**

The risks to the patient are limited to the minor risk of performing venipuncture and the risk of rejection with TAC-WD. The National Cancer Institute Common Terminology Criteria for Adverse Events v3.0 (CTCAE), dated December 12, 2003 will be used to grade all adverse (either serious or non-serious) events. It is the responsibility of the Principal Investigator to oversee the safety of the study. This safety monitoring will include careful assessment and appropriate reporting of adverse events as noted above. Medical monitoring will include a regular assessment of the number and type of serious adverse events. Information on all adverse events (signs, symptoms, abnormal diagnostic procedures, treatments) will be recorded in the appropriate adverse event module of the case report form (CRF). The clinical course of each event will be followed until resolution, stabilization, or until it has been determined that the study participation is not the cause. Serious adverse events that are still ongoing at the end of the study period will be followed to determine the final outcome.

Reports of all serious adverse events (including follow-up) will be submitted to the IRB within 24 hours of the investigator's knowledge of the event. Follow-up reports will be submitted to the IRB within 10 working days. The IRB/Office for the Protection of Research Subjects at NU is under the direction of [name]- [contact]. As this is a prospective study using primary data collection with a drug of interest all adverse events (AEs) – including serious adverse events (SAEs) and safety endpoints (where relevant) – will be collected and recorded in the study and safety database, irrespective of causal association. All adverse reactions identified will be reported to the local Health Authority in accordance with national regulatory requirements.

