## **10.3 Analysis of secondary objectives**

Clinical endpoints as correlates for the success and failure of TAC-WD/EVL will serve as secondary endpoints. This will include but not be limited to the following at 6 months ( $\pm$  1 month) post-LT: liver allograft and renal function, EVL & TAC side effects, infectious/malignant complications, and patient/graft survival. At study end, all secondary endpoints will be statistically compared between those who succeed or fail TAC-WD/EVL.

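### Section 7.3 defines the everolimus side-effect endpoint only in patients who succeed or stay on everolimus after rejection, and no analysis is specified for everyone who took the drug

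*Combined protocol and SAP*

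**What the plan says.** Section 7.3 names two sets for EVL side effects. The first is the "development of EVL side effects (hyperlipidemia, edema, proteinuria, etc) in those successfully withdrawn from TAC without rejection". The second concerns patients who cannot come off TAC because of rejection: "we will assess for TAC side effects and EVL side effects if this drug is continued following rejection".

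The synopsis is broader. Among the assessments after EVL is added it lists "EVL & TAC side effects and discontinuations", with no condition on outcome or on staying on the drug.

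Section 10.3 says "all secondary endpoints will be statistically compared between those who succeed or fail TAC-WD/EVL". Section 10.3.1 adds a mainly descriptive report that includes a rate of medication side effects, but does not say in whom. Section 10.1 forms groups by rejection alone, and 10.3.2 holds only the stopping rules.

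Data capture is not restricted. Section 7.2 has side effects of "everolimus (hyperlipidemia, edema, proteinuria, etc) will be documented in the case report forms". Section 7.4 says that all adverse events "will be collected and recorded in the study and safety database, irrespective of causal association". Section 8.1 asks about adverse events at each visit. For patients withdrawn early, 6.3.7 says "they will still be followed through the follow-up time period of the study as per standard medical care".

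**The concern.** Remaining on EVL is partly a result of tolerating it. A side-effect rate computed only in patients who reached a good outcome, or who were kept on the drug, has been filtered on the quantity it is meant to measure.

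The filter also operates earlier. The criteria in section 5.2 for starting TAC withdrawal require that the patient tolerates the combination and meets the month 1 to 2 criteria again. Those criteria list significant proteinuria (urine protein/creatinine ratio of at least 1.0) and cytopenias as contraindications to EVL. Proteinuria is also one of the EVL side effects named in 7.3. A patient who develops it to that degree cannot pass into the successfully withdrawn set.

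At stake is how the tolerability of EVL is described. The background gives tolerability as a reason to prefer EVL among the mTOR inhibitors. The success-versus-failure comparison of side effects is affected too, because patients who could not tolerate EVL have no stated place in it.

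**Working it through.** **Step 1: who is covered.** The table sets each type of EVL-treated patient against the text.

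| Patient | EVL side effects under 7.3 | Class in the 10.3 comparison |
|---|---|---|
| TAC withdrawn, no rejection, still on EVL | Yes, first set | Success |
| Rejection, EVL continued | Yes, second set | Failure |
| Rejection, EVL stopped | Not named | Failure |
| No rejection, EVL stopped for side effects before TAC withdrawal starts | Neither set | Not stated |
| No rejection, EVL stopped for side effects during or after TAC withdrawal | Neither set, unless being off TAC counts as success whatever happens to EVL; the text does not say so | Not stated |

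The last two rows cannot be settled from the definitions of success. Section 3.1 equates success with no rejection. Section 7.3 also requires no major complications, and the synopsis no other complications. The same patient could be a success under the first and a failure under the others.

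**Step 2: is there a figure to reproduce?** No. The documents give no expected EVL side-effect rate, no EVL discontinuation rate, and no power for this endpoint (10.4 and 10.5 say that a power analysis was not needed).

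**Step 3: size if the 7.3 sets were the denominator.** Inputs:

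- N, the number who start EVL. Section 10.4 plans 25 enrolled and 20 expected to undergo TAC withdrawal. Everyone in the 20 has started EVL, so N lies between 20 and 25 if that expectation holds.
- k, the number who stop EVL for side effects and fall outside both sets. Assumed 0, 1, 3 or 5.
- p, the side-effect rate in the remaining N − k. Assumed 0.2 to 0.5.

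The k omitted patients all had a side effect, so:

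- rate in all EVL starters = ((N − k)p + k)/N
- understatement = that rate − p = k(1 − p)/N

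Example with N = 25, k = 3, p = 0.3: (22 × 0.3 + 3)/25 = 9.6/25 = 38.4%, against 30% in the 7.3 sets. The difference is 3 × 0.7/25 = 8.4 points.

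Understatement in percentage points, for p from 0.5 down to 0.2:

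| k | N = 25 | N = 20 |
|---|---|---|
| 0 | 0 | 0 |
| 1 | 2.0 to 3.2 | 2.5 to 4.0 |
| 3 | 6.0 to 9.6 | 7.5 to 12 |
| 5 | 10 to 16 | 12.5 to 20 |

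If the rate is instead taken from the case report form and adverse event data on all patients, the understatement is zero whatever k is.

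**The case against.** The strongest reply is that nobody is left out. Side effects and adverse events are recorded for every patient, and those withdrawn early are followed so that they can be compared with completers. The rate in 10.3.1 is not confined to the 7.3 sets. The never-rejected group in 10.1 can hold patients who stop EVL without rejecting. The list of secondary endpoints in 10.3 is open-ended, so its silence on discontinuations does not exclude them. The clause on rejecters can be read as describing assessment after the rejection, without discarding what was recorded before it.

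Most of this stands. It rules out two stronger conclusions that a reader might draw from 7.3:

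- **That EVL side effects are assessed only in the two sets, so the reported rate is biased low.** The recording provisions contradict the first half. The second half depends on a denominator that 10.3.1 leaves open. Bias is possible but not established.
- **That the size can be read from the roughly 30% discontinuation quoted in the background.** That figure is for sirolimus, which the background ties to troughs of at least 8 ng/mL. The protocol's EVL target is 5 to 8 ng/mL. It is not an EVL rate and is not used here.

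The reply does not supply an analysis. The only place that says in whom EVL side effects are evaluated is 7.3, and it conditions on outcome. Section 6.3.7 says why data on withdrawn patients matter, yet section 10 plans no such comparison. The handling rule in 10.2.3 covers rejection and loss to follow-up, not stopping EVL for intolerance.

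**Conclusion.** The concern holds as a fault in the analysis set. As written, 7.3 evaluates EVL side effects in patients selected by outcome or by continued use. The comparison in 10.3 has no stated class for a non-rejecter who stops EVL, 10.3.1 has no denominator, and the synopsis is broader than all three. No analysis is specified for everyone who took EVL.

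If the 7.3 sets are used, the rate will tend to be low whenever patients stop EVL for side effects. The range of about 2 to 20 points for one to five such patients rests wholly on assumed k and p and on N of 20 to 25. It shows how far a handful of patients can move a rate in a trial this small and is not an estimate for this trial.

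This is a secondary, mainly descriptive outcome in a pilot whose follow-on trial is argued from biomarker prediction. The change is worth making because it is cheap, but the finding does not touch the primary endpoint.

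**What to change.** In 7.3, 10.3 and 10.3.1:

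- Report EVL side effects for every patient with at least one EVL dose, from EVL start to the end of that patient's study follow-up, with days on EVL as exposure.
- Report EVL discontinuations in the same set, with reason and timing, as an outcome in their own right.
- State how a patient without rejection who stops EVL is classed in the success-versus-failure comparison, and keep that comparison as a secondary display.
- Reconcile the synopsis, 7.3, 10.3 and 10.3.1 so that they name the same set and the same outcomes.

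The reporting period should not be cut at a fixed time after EVL is stopped. The four-week window in 8.2 runs from the end of study participation and serves SAE reporting, so it does not provide such a cut-off.

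The cost is wording. No new visits or data items are needed, because 7.2, 7.4 and 8.1 already collect the information and 6.3.7 keeps withdrawn patients under follow-up. The glossary describes premature withdrawal as the end of planned assessments and should be squared with 6.3.7 at the same time. The one downside for the sponsor is that the reported side-effect rate may be somewhat higher.
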